### 9.2 DATA ANALYSIS

Data analysis will be undertaken by members of the Research Study Team.

#### 9.2.1 ANALYSIS SET

Children aged 13-18 years (inclusive) self-administering AAI according to the study protocol. Analysis will be as treated.

#### 9.2.2 DEALING WITH MISSING VALUES

The reason for missing data will be indicated but missing data will not be imputed.

#### 9.2.3 SUPPLY OF DATA AND LOCKING OF THE DATABASE

Data will be entered into an excel database at Imperial College London. Data will be imported into Prism for analysis. Checks will be performed to ensure correct transfer. Once satisfactory the database will be locked.

#### 9.2.4 INTERIM ANALYSIS

No interim analyses are planned.

 [http://hedwig.mgh.harvard.edu/sample\\_size/js/js\\_crossover\\_quant.html](http://hedwig.mgh.harvard.edu/sample_size/js/js_crossover_quant.html)

## 9.3 STATISTICAL ANALYSIS PLAN

### 9.3.1 STATISTICAL PACKAGE

Prism (GraphPad Software Inc) version 7 or higher will be used.

### 9.2 SIGNIFICANCE LEVEL AND CONFIDENCE INTERVALS

95% confidence intervals will be reported. Where comparisons are made between sub-groups a 5% significance level will be used.

### 9.3 ANALYSES

Descriptive tables of numbers by age, gender, baseline variables and adverse events following AAI administration will be produced.

Paired data will be analysed, according to the paired difference between outcomes within the same individual between the different interventions, with all comparisons to data arising from Emerade 300mcg intervention. The planned analyses will therefore be:

- 1) Difference in peak plasma epinephrine ( $C_{max}$ ), time to  $C_{max}$  ( $T_{max}$ ), area under the plasma epinephrine versus time curve (AUC) between Emerade 300mcg and Emerade 500mcg.
- 2) Difference in peak plasma epinephrine ( $C_{max}$ ), time to  $C_{max}$  ( $T_{max}$ ), area under the plasma epinephrine versus time curve (AUC) between Emerade 300mcg (23mm needle) and Epipen 0.3mg (15mm needle).
- 3) Blood pressure, heart rate, stroke volume and change in PEFR versus plasma epinephrine concentrations over time after AAI administration (compared to both baseline and to Emerade 300mcg) will be explored using analysis of variance, analysis of covariance, and linear regression analyses.
- 4) Change in HRQL measures (FAQLQ, FAIM, self-efficacy) 1 month following each study visit, compared to baseline.

Other exploratory analyses:

- 1) Pharmacokinetic parameters of IM adrenaline injection ( $T_{1/2}$ , terminal elimination half-life;  $Cl$ , total body clearance;  $Vdss$ , volume of distribution at steady state) will be calculated from plasma epinephrine concentration versus time plots using Prism.
- 2) For the comparison between Emerade 300mcg (23mm needle) and Epipen 0.3mg (15mm needle), a sub-analysis of the difference in  $C_{max}$ ,  $T_{max}$  and AUC will be undertaken with reference to body weight, BMI and STMD.

Statistical differences will be determined using paired T-test for parametric data, or Wilcoxon signed-rank test for non-parametric data.

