## GLOSSARY OF ABBREVIATIONS

| ABBREVIATION | TERM   |
|--------------|--|
| AAI          | Adrenaline Auto Injector device  |
| ADR          | Adrenaline   |
| AE           | Adverse Event  |
| AUC          | Area under the curve. Derived from the drug concentration-time curve.                  |
| BP           | Blood pressure   |
| $C_{\max}$   | The post-dosing peak plasma concentration of a drug                                    |
| FAIM         | Food Allergy Independent Measure   |
| FAQL-Q       | Food Allergy Quality of Life - Questionnaire   |
| HR           | Heart rate   |
| HRQL         | Health Related Quality of Life   |
| IM           | Intramuscular  |
| PPI          | Patient and Public Involvement   |
| SAE          | Serious adverse event  |
| SAR          | Serious adverse reaction   |
| STMD         | Skin to Muscle Depth   |
| SV           | Stroke volume  |
| $T_{\max}$   | The time (in seconds) to reach $C_{\max}$  |
| $T_{1/2}$    | The time (in seconds) for the drug plasma concentration to reach half it's peak value. |
| USS          | Ultrasound   |

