## 5. STUDY TREATMENT

### 5.1 DESCRIPTION

- 1) Emerade 500 micrograms solution for injection in pre-filled pen. Emerade 500 micrograms delivers a single dose of 0.5 ml containing 500 micrograms of adrenaline (as tartrate).
- 2) Emerade 300 micrograms solution for injection in pre-filled pen. Emerade 300 micrograms delivers a single dose of 0.3 ml containing 300 micrograms of adrenaline (as tartrate).
- 3) EpiPen® Adrenaline (Epinephrine) Auto Injector 0.3 mg.

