### 5.2 DOSAGE AND ROUTE OF ADMINISTRATION

0.3-0.5ml intramuscular injection, to be administered according to the SmPC provided.

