**6. STUDY VISITS, PROCEDURES SCHEDULE and PATIENT FLOW DIAGRAM**

The study is summarised in Figure 2:

**Figure 2:** Study Flowchart

Following eligibility assessment (which can be done via telephone or in clinic), participants will be randomised to attend for either:

- 2 x self-administered doses of 300mcg adrenaline (given 4 hours apart), or
- 1 x self-administered dose of 500mcg adrenaline (given using an Emerade 500 device).

These study visits will happen one month apart. On the day when 2 doses of 300mcg adrenaline are administered, the order of devices used (Epipen 0.3mg, Emerade 300mcg) will also be randomised. The randomisation will follow a balanced, randomized-block crossover design, as follows:

| Study visit 1 |                | Study visit 2  |                |                |
|---------------|----------------|----------------|----------------|----------------|
|               | Morning        | Afternoon      | Morning        |                |
| 1             | Emerade 300mcg | Epipen 0.3mg   | Emerade 500mcg | -              |
| 2             | Epipen 0.3mg   | Emerade 300mcg | -              | Emerade 500mcg |
| 3             | Emerade 500mcg | -              | Emerade 300mcg | Epipen 0.3mg   |
| 4             | -              | Emerade 500mcg | Epipen 0.3mg   | Emerade 300mcg |

**Figure 3:** Randomisation table

This randomisation process is designed to reduce the influence of circadian variations on endogenous adrenaline levels and assess any impact of the order of administration of the 300mcg devices. The randomisation list will be generated using an online randomisation tool (<http://www.randomization.com>).

To reduce participant inconvenience, where eligibility has been confirmed, randomisation may occur prior to consent in order to arrange study visits to suit the participant and their family. In such an event, consent will be obtained prior to any intervention at the first study visit.

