#### 6.2.3.3 BLOOD SAMPLING AND PROCESSING

4ml blood samples (plasma) will be obtained from the venous cannula at the following timepoints AFTER self-injection: 5, 10, 15, 20, 30, 45, 60, 80, 100, 120 and 180 minutes. A maximum of 2.5ml/kg blood will be withdrawn during each study visit. Oral fluid intake will be encouraged and intake volumes monitored.

Blood samples will be taken into sealed Lithium Heparin tubes and immediately put on ice. They will then be transferred at the earliest opportunity to an on-site sample processing laboratory and centrifuged at 2500g, 4°C for 15 mins, then aliquoted and snap frozen at -80°C. Samples will be batched and then transferred on dry ice to the Department of Clinical Biochemistry at the Royal Brompton Hospital for catecholamine measurement.

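### Exploratory item 1 plans total body clearance, Vdss and elimination half-life from intramuscular doses alone, which give only CL/F and an apparent terminal half-life

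*Combined protocol and SAP*

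**What the plan says.** Exploratory item 1 in section 9.3 (Analyses) names three parameters: T1/2, spelled out as "terminal elimination half-life"; Cl, spelled out as "total body clearance"; and Vdss. The sentence closes "volume of distribution at steady state) will be calculated from plasma epinephrine concentration versus time plots using Prism". The item is headed as concerning intramuscular injection, but none of the three is called apparent.

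Section 5.1 lists three auto-injectors. Section 5.2 gives one route: "intramuscular injection, to be administered according to the SmPC provided". In the randomisation table in section 6, each sequence consists of two 300 mcg injections four hours apart on one day and a single 500 mcg injection on the other. No sequence includes an intravenous dose, and no value or assumption for F or for absorption time is given.

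Section 6.2.3.3 sets the sampling: "timepoints AFTER self-injection: 5, 10, 15, 20, 30, 45, 60, 80, 100, 120 and 180 minutes". No rule is stated for AUC beyond 180 min or for handling endogenous adrenaline in AUC.

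The glossary defines T1/2 differently, as the time, in seconds, "for the drug plasma concentration to reach half it's peak value".

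**The concern.** Clearance, volume at steady state and elimination half-life describe what the body does with drug already in the circulation. After an extravascular dose, the plasma curve mixes that with how much drug arrived and how fast. Without an intravenous reference or a known F and absorption time, the two cannot be separated.

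Followed as written, item 1 would put values for adolescents on record under names that the data cannot support. The trial's own rationale makes this relevant. Section 1.1 says that a needle shorter than the skin-to-muscle depth may deliver the dose subcutaneously, so absorption may differ by device. If the parameters were tabulated by device, a within-person difference in Cl or Vdss could come from absorption or F and be misread as altered disposition.

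The glossary raises a smaller, separate matter: one symbol carries two meanings.

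**Working it through.** The plan gives no figure for these parameters. Its only design calculation, a detectable difference of 0.35 pg/ml in section 9.1, reproduces (0.350 pg/ml with n = 12, SD of the difference 0.39, 10 degrees of freedom, 80% power, two-sided 0.05) but does not bear on this point.

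**Inputs.** From the documents: intramuscular route, dose D, 11 sampling times ending at 180 min, and four hours between same-day doses. Assumed for illustration only: F, all half-lives and the endogenous baseline level.

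**Model.** One compartment with first-order absorption: C(t) = F·D·ka / [V(ka − ke)] × (exp(−ke·t) − exp(−ka·t)). Pairs below are absorption/elimination half-lives.

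**1. Clearance.** AUC = F·D/CL, so D/AUC = CL/F. Calling this total body clearance overstates it by 1/F: 1.00, 1.33 and 2.00 times for assumed F = 1, 0.75 and 0.5.

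**2. Half-life.** Exchanging ka and ke and setting V′ = V·ke/ka leaves C(t) unchanged. For 20/10 min, ke/ka = 20/10 = 2, so the twin is 10/20 min with volume 2V. At 20 min:
- 20/10 with V: ka/(ka − ke) = −1, so C = −1 × (0.25 − 0.50) = 0.25 F·D/V.
- 10/20 with 2V: ka/(ka − ke) = 2, so C = (2/2) × (0.50 − 0.25) = 0.25 F·D/V.

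The maximum relative difference is 0 at all 11 sampling times. The terminal half-life is 20 min in both cases, but elimination half-life is 10 min in one and 20 min in the other.

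**3. Vdss.** Vss = F·D·(MRT − MAT)/AUC, where MRT is mean residence time and MAT is mean absorption time. For both curves MRT = 1/ka + 1/ke = 30/ln 2 = 43.3 min. MAT is 20/ln 2 = 28.9 min or 10/ln 2 = 14.4 min, leaving 14.4 or 28.9 min, so the same data fit volumes 2-fold apart. If F may be 1 or 0.5, the span is 4-fold. Leaving MAT out gives (V/F)(1 + ke/ka). With F = 1 that is 3 times the true volume for 20/10 (1 + 2) and 1.5 times for 10/20 (1 + 0.5).

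**4. AUC after 180 min.** Share = (ka·exp(−180ke) − ke·exp(−180ka))/(ka − ke). The factor is 1/(1 − share).

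| Half-lives (min) | Share of AUC after 180 min | CL/F from AUC(0–180) overstated by |
|---|---|---|
| 5/10 | 0.0% | 1.00 |
| 20/10 | 0.4% | 1.00 |
| 40/10 | 5.9% | 1.06 |
| 60/10 | 15.0% | 1.18 |

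**5. Extrapolating without baseline subtraction.** The tail term, last concentration divided by terminal slope, assumes decay to zero, whereas adrenaline is endogenous. I added a constant baseline as a share of the exogenous peak and took the slope from the last three samples.

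| Half-lives (min) | Assumed baseline | Extrapolated AUC ÷ true drug AUC | AUC(0–180) ÷ true drug AUC |
|---|---|---|---|
| 5/10 | 5% | 3.50 | 1.31 |
| 5/10 | 2% | 1.49 | 1.12 |
| 20/10 | 5% | 1.24 | 1.16 |

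In the last row the fitted terminal half-life is about 53 min, against a true 20 min. Extrapolating uncorrected data can therefore be worse than not extrapolating.

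**6. Second dose on the same day.** The same share formula at 240 min puts 7.5% of the morning dose's AUC after the afternoon injection for 60/10, and under 0.1% for 5/10 and 20/10.

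**7. The two T1/2 definitions.** For 5/10 the peak is at 10.0 min and half-peak at 27.7 min from dosing, which is 17.7 min after the peak. The terminal half-life is 10 min. The glossary does not say which starting point applies.

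**The case against.** The strongest reply is that this is largely terminology in an exploratory list. Item 1 declares the intramuscular route, so a pharmacokineticist would read the values as apparent, and assuming F = 1 would make Dose/AUC equal to clearance. That is fair as far as it goes. But the plan neither states F = 1 nor calls anything apparent, and F = 1 would rescue only clearance. Vdss would still need the absorption time, and nothing would show that the terminal slope is elimination.

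A second reply is that every magnitude above comes from assumed inputs. That stands: the 2-fold and 4-fold figures follow from the values chosen and do not estimate the error in this trial. The lack of identifiability does not depend on them.

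A third is that the T1/2 conflict has little practical effect, because section 9.3 defines the symbol where it is used. That also stands. An analyst following section 9.3 has one definition, and the glossary needs only a correction.

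A reader might infer that the dose or needle-length comparison is undermined. The documents do not support that. Sections 2 to 3.1.2 name none of these three parameters as an objective, hypothesis or outcome, and the paired comparisons of Cmax, Tmax and AUC are separate planned analyses that do not use them.

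**Conclusion.** Minor, but wrong as written. From intramuscular data alone, item 1 can deliver CL/F and an apparent terminal half-life that may reflect absorption. It cannot deliver total body clearance without F, an elimination half-life without knowing which process limits the terminal slope, or Vdss without both F and the absorption time. This rests on the route and the absence of an intravenous reference, both plain in the documents, and not on the illustrative values.

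The size of error in this trial cannot be given. Nor do the documents show that truncation at 180 min is material: in the illustration it is negligible in two of four cases and matters only if absorption is slow.

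**What to change.** Replace exploratory item 1 in section 9.3 (Analyses) with:

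> Apparent clearance (CL/F) and apparent terminal half-life (may be absorption-limited) will be calculated from concentrations after subtracting the pre-dose baseline value; Vdss will not be reported. CL/F will use AUC extrapolated beyond 180 min only on baseline-subtracted data, with the extrapolated share reported; otherwise AUC(0–180) will be used and labelled as such. On the two-dose day, any carry-over from the morning dose into the afternoon profile will be noted when interpreting the afternoon values.

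In the glossary, replace the T1/2 entry with the revised term, apparent terminal half-life. If time to half-peak is wanted, give it its own symbol and state whether it runs from dosing or from the peak.

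The new text needs a pre-dose value. The Medical Assessment section (6.2.2, item 7) implies a baseline sample after cannulation, but section 6.2.3.3 lists only post-injection times, and neither says whether a fresh baseline precedes the afternoon injection. State which value is subtracted for each dose.

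The cost is wording and one lost exploratory parameter. The listed post-injection times, the sample size and the planned Cmax, Tmax and AUC comparisons stay as they are.

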### 4.3 SUBJECT WITHDRAWAL

Parents/guardians may withdraw their child at any time without giving a reason. In accordance with the current revision of the Declaration of Helsinki and any other applicable regulations, the parents or legal representatives of the child have the right to withdraw the participant from the study at any time and for any reason, without prejudice to his or her future medical care, and are not obliged to give his or her reasons for doing so.

The investigator may withdraw a participant from the study at any time if, in the investigator's clinical judgment, it is in the best interests of the participant's health and well-being. In addition the participant may be withdrawn for any of the following reasons:

- Decision by the Investigator
- Ineligibility (either newly arising during the study, or retrospective having been overlooked at screening)
- Significant protocol deviation where this will impact irreversibly on data integrity  
e.g. failure to administer adrenaline autoinjector correctly
- Participant non-compliance with study requirements
- An adverse event which requires discontinuation of the study treatment, or results in inability to continue to comply with study procedures.

If the participant is withdrawn due to an adverse event, the Investigator will arrange for appropriate follow-up through telephone calls (and/or visits if necessary) until the adverse event has resolved or stabilised.

Any data generated from monitoring or samples already taken from a withdrawn participant will be included in the data analyses, unless specific instruction for their destruction is received from the participant or their parent/guardian. Withdrawn participants will be replaced, where feasible.

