## 9. STATISTICS AND DATA ANALYSIS

### 9.1 SAMPLE SIZE ESTIMATION

This is an exploratory analysis to assess the pharmacokinetics/pharmacodynamics of self-injection of adrenaline in young people with IgE-mediated food allergy. Existing PK/PD studies have not, in general, used a crossover design, but a parallel design with sample size from 5-9 participants per study arm.

In this study, with a cross-over design and a sample size of 12, we expect to detect, with 80% power, a treatment difference of 0.35pg/ml at a two-sided 0.05 significance level (this is based on pilot data (n=55) where the standard deviation of the difference between baseline plasma adrenaline levels on 2 separate occasions in the same individuals was 0.39 pg/ml). In a previous parallel-design study comparing EpiPen 0.15mg to 0.3mg, the latter dose was associated with plasma levels of, on average, >500pg/ml. We therefore expect a sample size of 12 should provide sufficient power to detect any difference in plasma catecholamine levels following AAI administration due to differences in dose or needle length.

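### The planned paired tests leave out the order factors that Figure 3 randomises: a visit term for 500mcg vs Emerade 300mcg, and a half-day/order term for EpiPen vs Emerade 300mcg

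*Combined protocol and SAP*

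**What the plan says.** Section 6 assigns participants to four sequences (Figure 3) and gives the reason: "This randomisation process is designed to reduce the influence of circadian variations on endogenous adrenaline levels". The same sentence adds a second purpose, to see whether the order in which the two 300mcg devices are used matters.

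Section 9.3 (Analyses) compares Cmax, Tmax and AUC within person: "Paired data will be analysed, according to the paired difference between outcomes within the same individual between the different interventions", always against Emerade 300mcg. The tests are named once: "Statistical differences will be determined using paired T-test for parametric data, or Wilcoxon signed-rank test for non-parametric data". For intervals, the plan says "95% confidence intervals will be reported". No visit, sequence or half-day term appears. The analyses of variance, covariance and regression in item 3 of 9.3 concern blood pressure, heart rate, stroke volume and peak flow, and name no order term either.

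On dropouts, section 4.3 says "Withdrawn participants will be replaced, where feasible". It does not say which sequence a replacement receives.

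**The concern.** A one-sample test on paired differences treats all 12 differences as draws from one distribution. If outcomes shift between visits, or between the first and second half of the day, the differences come from two distributions with different means, one per order group. The balanced table keeps the overall mean right, but the spread between the two groups is counted as random error. Section 1.2 chose the crossover to gain power. With 12 participants, a real dose or device difference could be missed, or reported less precisely than the data allow.

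The balance is also not protected. If withdrawals leave the order groups unequal, the shift no longer averages out and part of it moves into the estimate.

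**Working it through.** **1. Which effect enters which contrast.** The last column of Figure 3 has no heading in the text available; I read it as the afternoon of visit 2, following the row layout. Let v be the visit 2 minus visit 1 shift and w the afternoon minus morning shift, both additive. On the day with two 300mcg doses, afternoon is also second injection, so w carries both.

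| Sequence | Emerade 500 | Emerade 300 | EpiPen | 500 − Emerade 300 | EpiPen − Emerade 300 |
|---|---|---|---|---|---|
| 1 | visit 2, am | visit 1, am | visit 1, pm | τ + v | δ + w |
| 2 | visit 2, pm | visit 1, pm | visit 1, am | τ + v | δ − w |
| 3 | visit 1, am | visit 2, am | visit 2, pm | τ − v | δ + w |
| 4 | visit 1, pm | visit 2, pm | visit 2, am | τ − v | δ − w |

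The two Emerade doses always share a half-day, so an additive time-of-day effect cancels in the dose contrast. The two 300mcg devices always share a visit, so v cancels in the device contrast. Each contrast is exposed to one effect.

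**2. The plan's own figure.** Section 9.1 claims 80% power for 0.35 pg/ml with 12 participants and a two-sided 5% test, taking as its input that "the standard deviation of the difference between baseline plasma adrenaline levels on 2 separate occasions in the same individuals was 0.39 pg/ml". SE = 0.39/√12 = 0.1126 and 0.35/0.1126 = 3.11. Noncentral t:
- 11 df (paired t): power 80.8%, detectable difference 0.347.
- 10 df (crossover with a period term): power 80.0%, detectable difference 0.350.

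Both agree with the stated 0.35 and 80%.

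**3. Interval width.** Let p be the order effect (v or w) in SDs of the paired difference, with 6 participants per order group. The variance seen by the paired test has expectation SD²(1 + p² × 12/11).
- Planned half-width: t(11) × SD × √[(1 + 12p²/11)/12], t(11) = 2.201.
- Adjusted half-width: t(10) × SD/√12, t(10) = 2.228.

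With SD = 0.39 the adjusted half-width is 0.251 pg/ml for any p. The planned one is 0.248 at p = 0, 0.256 at 0.25, 0.280 at 0.5 and 0.358 at 1. Break-even: 12p²/11 = (2.228/2.201)² − 1 = 0.0248, so p ≈ 0.15.

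**4. Power.** Simulation of the t-tests, 200,000 trials per setting, 6:6 groups, true difference 0.889 SD (0.347/0.39), where the paired t-test has 80% power with no order effect:

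| p (assumed) | CI width ratio, formula | CI width ratio, simulated | Power, paired | Power, adjusted |
|---|---|---|---|---|
| 0 | 0.99 | 0.99 | 80% | 79% |
| 0.25 | 1.02 | 1.02 | 78% | 79% |
| 0.5 | 1.11 | 1.12 | 72% | 79% |
| 0.75 | 1.26 | 1.26 | 62% | 79% |
| 1 | 1.43 | 1.44 | 48% | 79% |

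Simulating the four sequences with 3 participants each confirms step 1. A visit effect of 0.5 SD widens only the dose contrast (half-width 0.70 against 0.63 SD adjusted). A half-day effect of 0.5 SD widens only the device contrast, by the same amount. Coverage of the planned interval is about 97% at 0.5 SD and 99% at 1 SD.

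**5. Unequal groups.** The unadjusted estimate moves by p × (n₁ − n₂)/(n₁ + n₂): 1/11 = 9% of the effect at 6:5, 2/12 = 17% at 7:5, 4/12 = 33% at 8:4. At 8:4 and p = 0.5 the simulated bias is 0.17 SD for the planned analysis and none for the adjusted one.

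**The case against.** A reader might infer that circadian variation is put back as noise into the primary comparison. The documents do not support that: Figure 3 places both Emerade doses in the same half-day in every sequence, so for 500 vs 300 the circadian control works even under the paired test. Only a visit effect is left there.

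A reader might also infer that the planned intervals are too wide. That depends on an effect whose size the documents never give. Below about 0.15 SD the planned interval is as narrow or slightly narrower, and at 0.25 SD the power loss is about 1 point. The 1 SD case needs an order effect larger than the treatment difference being sought (0.889 SD). The protocol also limits such shifts: caffeine avoidance, a wait of at least 30 minutes after cannulation, semi-recumbent rest and a 2-hour fast.

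The loss shrinks when the true difference is large. At 0.5 SD of order effect, power is 93.7% vs 96.1% for a difference of 1.2 SD, and 99.3% vs 99.6% for 1.5 SD. The study calls itself exploratory.

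All of this stands, and it limits the point to precision: with balanced groups the planned test is valid. What it does not answer is that adjusting costs almost nothing, that nothing in 4.3 keeps the groups equal, and that the stated aim on device order has no analysis. An 8:4 split is unlikely, though; it needs at least two withdrawals from one order group with both replacements placed in the other.

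**Conclusion.** The omission is real, and its consequence is conditional. Section 9.3 lacks a visit term for 500 vs Emerade 300 and a half-day/order term for EpiPen vs Emerade 300. If the relevant effect exceeds about 0.15 SD of the paired difference, the planned interval is wider than necessary and power at the detectable difference falls, by about 1 point at 0.25 SD, 7 at 0.5 SD and 31 at 1 SD. The planned analysis does not inflate type I error while the groups are equal; at 1 SD its true level is about 0.7%.

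This rests on additive effects, the t-test rather than the Wilcoxon, an assumed range of 0 to 1 SD, and the reading of Figure 3 above. The 0.39 pg/ml is for baseline adrenaline, not post-dose Cmax or AUC, so the ratios are more informative than the absolute widths.

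It would be wrong to infer that the adjustment secures the 500 vs 300 contrast against every order effect. Emerade 300 is the second injection of the day in sequences 2 and 4; Emerade 500 never is. A second-injection effect of 0.5 SD biases that contrast by 0.25 SD with or without a visit term. The 79% assumes no such effect.

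**What to change.** In 9.3, replace the paired test for Cmax, Tmax and AUC by the order-adjusted crossover analysis:
- **500 vs Emerade 300:** take each participant's visit 2 minus visit 1 difference and compare sequences 1+2 with 3+4.
- **EpiPen vs Emerade 300:** take each participant's afternoon minus morning difference and compare sequences 1+3 with 2+4.
- Use an unpaired t-test on 10 df, or a rank-sum test for non-parametric data. Report half the group difference as the treatment effect, with its 95% CI.
- For the 300mcg devices, also report the average of the two group means. This estimates the half-day/order effect and supplies the missing analysis for the aim in section 6.

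In 4.3, state that a replacement takes the sequence of the participant replaced.

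The change is wording only. The data are those already planned and both tests run in Prism. If there is no order effect, the cost is one degree of freedom: an interval about 1% wider (2.228/2.201 = 1.012) and under 1 point of power. The stated 0.35 pg/ml keeps 80.0% power on 10 df. Specify it before the data are seen. A second-injection or carry-over effect on 500 vs 300 needs separate handling.
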